### 10.2 STATISTICAL HYPOTHESES

Participants will be categorized as impaired, not impaired or indeterminate/intermediate for each of DCTclock, MMSE, and MoCA using the first measurement obtained on each participant. A 3-by-3 table, with the rows being the DCTclock/MMSE cognitive status and with columns being the MoCA cognitive status, will be generated as follows.

		MoCA			
		Impaired	Indeterminate/Intermediate	Unimpaired	Total
DCTclock/ MMSE	Impaired	a	b	c	a+b+c
	Indeterminate/ Intermediate	d	e	f	d+e+f
	Unimpaired	g	h	i	g+h+i
	Total	a+d+g	b+e+h	c+f+i	a+b+c+d+e+f+g+h+i

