### 10.4.3 SAMPLE SIZE

Approximately 500 participants will be enrolled to obtain 400 evaluable participants. The evaluable sample size is the same as the evaluable sample size used in “De Novo Classification Request for Cognivue”. The primary null and alternative hypotheses are:

$$H_0: \kappa \leq 0.40 \quad \text{vs.} \quad H_1: \kappa > 0.40$$

where  $\kappa$  is the quadratic weighted kappa statistic calculated from the above DCT-MMSE classification table. Power for quadratic weighted kappa requires assumptions of the values on the diagonal and off-diagonal of the table, which is a large number of assumptions. Power will thus be calculated for the unweighted kappa which requires fewer assumptions. It is assumed that the quadratic weighted kappa will be similar to or larger in magnitude than the unweighted kappa and with similar standard error as the unweighted kappa, so the study will be powered to show that the unweighted kappa  $> 0.4$  with the expectation it will then be sufficiently powered to show that the quadratic weighted kappa  $> 0.4$ . An evaluable sample size of 400 subjects yields at least 80% power to reject the above null hypothesis at one-sided 0.025 level of significance under the assumptions that: (1) the true kappa is 0.52 or more; (2) the marginal percentage of participants categorized as impaired is between 20% and 42.5% for DCTclock; (3) the marginal percentage of participants categorized as impaired for MMSE is the same as that for DCTclock; (4) the marginal percentage of participants categorized as unimpaired for DCTclock is the same as the marginal percentage of participants categorized as impaired for DCTclock; (5) the marginal percentage of participants categorized as unimpaired for MMSE is the same as that for DCTclock; and (6) the marginal percentage of participants categorized as indeterminate is between 15% and 60% for each of DCTclock and MMSE and is equivalent between DCTclock and MMSE.

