#### 10.4.10 SUB-GROUP ANALYSIS

All above effectiveness analyses (with the exception of the formal hypothesis test of the weighted kappa) may be repeated by (1) age (below median age, at or above median age); (2) sex; (3) education level; (4) language fluency test score (below median, at or above median) (5) medical history; and (6) current medications.

In addition, it is expected that the DCTclock test’s ability to identify impaired participants exceeds that of MMSE when participants are mildly impaired. Thus, for participants who score unimpaired on MMSE but impaired on DCTclock, scores on the neuropsychology battery test may be further inspected as follows to assess how often the DCTclock yielded the correct diagnosis in these cases. Specifically, the following will be presented on this subset of participants (when available):

- Percentage of participants scoring in the impaired range on the MoCA test (25 or below)
- Percentage of participants scoring 1.5 standard deviations below the mean on two or more of the following tests (Benton Judgement of Line, Rey Complex Figure, DKEFs, Digit Span, Blocks, Trails, Symbol Digit).
- Percentage of participants 2 standard deviations below the mean on one of the following tests (Benton Judgement of Line, Rey Complex Figure, DKEFs, Digit Span, Blocks, Trails, Symbol Digit).

---

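### The subset meant to examine what MMSE misses in mild impairment leaves out every DCTclock-impaired participant whom MMSE places in the middle category

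*Protocol*

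**What the plan says.** Section 10.4.10 states that "it is expected that the DCTclock test’s ability to identify impaired participants exceeds that of MMSE when participants are mildly impaired". From that expectation it derives a check "for participants who score unimpaired on MMSE but impaired on DCTclock": for this group, "scores on the neuropsychology battery test may be further inspected as follows", in order to see how often DCTclock was right. Three percentages are listed: MoCA in the impaired range; 1.5 SD below the mean on at least two battery tests; and 2 SD below on one battery test.

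The classification behind this has three levels. Section 10.2: "Participants will be categorized as impaired, not impaired or indeterminate/intermediate for each of DCTclock, MMSE, and MoCA".

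The middle level is not assumed to be rare. Section 10.4.3 takes it that "the marginal percentage of participants categorized as indeterminate is between 15% and 60% for each of DCTclock and MMSE".

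The agreement formulas in 10.4.4 and 10.4.5 show how the plan treats that level elsewhere. Positive percent agreement is a/(a+d+g), where d is an indeterminate row result in a person whom the column classification calls impaired. Negative percent agreement is (e+f+h+i)/(b+c+e+f+h+i), where e and f are indeterminate row results.

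**The concern.** The stated question is whether DCTclock identifies impaired people whom MMSE does not. On a three-level scale MMSE can fail to call someone impaired in two ways: by an unimpaired result or by an indeterminate/intermediate one. The rule in 10.4.10 keeps the first and drops the second, and gives no reason.

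This sits badly with the plan's own formulas. In positive percent agreement, cell d counts in the denominator but not in the numerator, so an indeterminate MMSE result in a MoCA-impaired person is a miss. In negative percent agreement, e and f count in the numerator, so an indeterminate result is grouped with not impaired. The plan therefore treats an indeterminate MMSE result as not identifying impairment, and then excludes such results from the subset built to look at what MMSE fails to identify.

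At stake is whether the percentages answer the question that introduces them. They would describe only the two-category disagreements, possibly very few people, and say nothing about one-category disagreements on which the same data are collected.

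**Working it through.** **Inputs, all from section 10.4.3 unless noted.** Evaluable n = 400; true unweighted kappa between DCTclock and MMSE k = 0.52 (the plan says this or more); null kappa 0.40; impaired share p from 20% to 42.5%; unimpaired share equal to p; indeterminate share 1 − 2p, hence 60% to 15%; same margins for both tests. The plan gives no size for the subset and no off-diagonal cells. It also assumes that quadratic weighted kappa is similar to or larger than unweighted kappa.

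**Step 1: the plan's own figure.** "An evaluable sample size of 400 subjects yields at least 80% power" at "one-sided 0.025 level of significance". With the large-sample standard error of unweighted kappa and power = Φ((0.12 − 1.96·SE₀)/SE₁), power is 82% to 93% over the stated margins. It is lowest at p = 20%: 85.2% with proportional disagreement and 82.1% with the latent-normal model. The stated figure holds, so the inputs are being read as intended.

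**Step 2: two ways to fill the off-diagonal cells.** Write a for the cell DCTclock impaired / MMSE indeterminate (omitted) and c for DCTclock impaired / MMSE unimpaired (kept). The omitted share is a/(a + c).

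- *Proportional disagreement:* a = (1 − k)·p·(1 − 2p) and c = (1 − k)·p². The share is (1 − 2p)/(1 − p), whatever the kappa.
  - At p = 0.20: a = 0.48 × 0.20 × 0.60 = 0.0576, or 23.0 of 400; c = 0.48 × 0.20² = 0.0192, or 7.7. Share = 0.60/0.80 = 75%.
  - At p = 0.425: a = 0.48 × 0.425 × 0.15 = 0.0306, or 12.2; c = 0.48 × 0.425² = 0.0867, or 34.7. Share = 0.15/0.575 = 26%.
- *Latent bivariate normal:* cut-points at the margins, correlation solved so that k = 0.52 (about 0.82 to 0.84).

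| Impaired (indeterminate) | Proportional: omitted / kept / share omitted | Latent normal: omitted / kept / share omitted |
|---|---|---|
| 20% (60%) | 23.0 / 7.7 / 75% | 26.8 / 0.1 / 99.7% |
| 30% (40%) | 23.0 / 17.3 / 57% | 31.0 / 1.3 / 96% |
| 40% (20%) | 15.4 / 30.7 / 33% | 26.0 / 9.5 / 73% |
| 42.5% (15%) | 12.2 / 34.7 / 26% | 22.1 / 14.9 / 60% |

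**Step 3: what the plan's assumptions allow.** In a symmetric table, kappa fixes 4a + 2c = (1 − k)(4p − 6p²), and quadratic weighted kappa equals 1 − (a + 2c)/p. If weighted kappa is at least k, then a + 2c ≤ (1 − k)p. Subtracting gives 3a ≥ (1 − k)(3p − 6p²), so a ≥ (1 − k)·p·(1 − 2p). That bound is the proportional value. The omitted share in symmetric tables is therefore 75% to 100% at p = 20% and 26% to 100% at p = 42.5%. If weighted kappa may fall below 0.52, the margins and kappa set no useful lower bound.

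**Step 4: size after widening.** DCTclock impaired and MMSE not impaired gives about 31 to 47 of 400 under proportional disagreement (against 8 to 35 as planned), and about 27 to 37 under the latent-normal model (against 0.1 to 15).

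**Step 5: a further limit on numbers.** Sections 7.1.1 and 7.3.4 give Benton, Rey, D-KEFs, Block Designs and Symbol Digit only to participants who completed visit 1 under protocol version 1. Two of the three percentages draw on those tests, so their denominators may be smaller than the cell counts above.

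**The case against.** The rule can be defended. An intermediate MMSE result is not a clean pass, so restricting the check to outright contradictions isolates the unambiguous MMSE misses. The plan is also not uniform about the middle level: 10.4.5 repeats a kappa analysis with that group omitted. And the check is optional and descriptive, with no success criterion. This stands as a reason to keep the planned cell visible and to rate the point as minor. It does not explain why the adjacent cell goes unreported, since the protocol offers no such rationale.

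Two stronger readings are tempting and are not supported:

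- *That the plan's own figures imply a loss of 60% to 99%.* That range needs the latent-normal model, which the protocol does not state. Section 10.4.3 powers on unweighted kappa in order to avoid assumptions about the cells. Proportional disagreement meets the same assumptions and gives 26% to 75%. With 40% or 42.5% impaired, the planned cell is then the larger of the two.
- *That mildly impaired people fall mainly in the MMSE-intermediate cell, so that the rule picks the wrong people.* The protocol sections on classification give no MMSE or DCTclock cut-offs and no definition of mild impairment. If MMSE does miss mild impairment, as 10.4.10 expects, such people may well score unimpaired on it.

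The equal margins in 10.4.3 also leave no room for the DCTclock advantage that 10.4.10 expects. The counts above illustrate scale and are not forecasts.

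**Conclusion.** The point holds in a limited form. Read literally, 10.4.10 inspects one of the two cells in which DCTclock says impaired and MMSE does not. The omission fits poorly with the stated aim and with the plan's own agreement formulas.

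The omitted share is about 26% to nearly 100%. This rests on n = 400, kappa 0.52, the stated equal margins, symmetric tables and weighted kappa no lower than unweighted; where it falls within that range depends on an assumed pattern of disagreement. The denominator is all DCTclock-impaired, MMSE-not-impaired participants, not confirmed cases of mild impairment.

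The primary test and its power are untouched. Section 10.1 leaves detail to a statistical analysis plan that was not available for this check, so the finding concerns what 10.4.10 itself fixes. It is a minor but worthwhile correction.

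**What to change.** In 10.4.10, define the subset as participants impaired on DCTclock and not impaired on MMSE, meaning indeterminate/intermediate or unimpaired. Present the three listed percentages separately for the two MMSE cells. Give each its n, counting only those with the required tests, and a 95% CI (Wilson, as elsewhere in the plan). Do not label either cell in advance as the one that represents mild impairment.

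If only the opposite-result cell is really wanted, say why, and remove the link to mild impairment.

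The cost is one reworded sentence and one extra column in a descriptive table, with no new data. The small downside is that the added cell may give a less favourable result.

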### 7.1.1 STUDY SPECIFIC PROCEDURES

- Demographics and review of medical history and current medications
- Assessment of impairment of the dominant hand
- Assessment of recreational drug or alcohol use
- Reading and comprehension assessment
- Hamilton-Veale Contrast Sensitivity
- DCTclock
- Purdue Peg Board
- MMSEworld
- MoCA
- Benton Judgement of Line Orientation\*
- Rey Complex Figure\*
- D-KEFs Verbal Fluency (sub-test of D-KEFs)\*
- Digit Span and Reliable Digit Calculation (sub-test of WAIS-IV)
- Block Designs (sub-test of WAIS-IV)\*
- Trail Making Test – Parts A and B
- Symbol Digit Modalities\*
- Geriatric Depression Scale (15 item version)\*

Assessments indicated with an asterisk (\*) above will only be given to participants who complete visit 1 under protocol version 1.

No results from these assessments will be provided to the participant.

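### Section 10.4.10 reads the share meeting a multi-test battery rule as how often DCTclock was right, with no comparison group and no rule for participants given only two of the seven tests

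*Protocol*

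**What the plan says.** Protocol section 10.4.10 states an expectation that DCTclock finds mild impairment better than MMSE does. It then says that, "for participants who score unimpaired on MMSE but impaired on DCTclock", "scores on the neuropsychology battery test may be further inspected as follows", and gives the purpose as "to assess how often the DCTclock yielded the correct diagnosis in these cases".

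Three percentages follow, for this subset only:
- the share in the impaired range on MoCA;
- "Percentage of participants scoring 1.5 standard deviations below the mean on two or more of the following tests";
- "Percentage of participants 2 standard deviations below the mean on one of the following tests".

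The last two use the same seven tests: "Benton Judgement of Line, Rey Complex Figure, DKEFs, Digit Span, Blocks, Trails, Symbol Digit". The section does not say whose mean and SD apply, and it names no comparison subset.

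The only allowance for tests not taken is that "the following will be presented on this subset of participants (when available").

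Sections 7.1.1, 7.3 and 7.3.4 cut the battery after version 1. Asterisked tests "will only be given to participants who complete visit 1 under protocol version 1". Five of the seven carry the asterisk: Benton, Rey, D-KEFs, Block Designs and Symbol Digit. Digit Span and Trails remain.

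**The concern.** A rule that is met by one low score among several tests is met by some unimpaired people, and more often as the number of tests grows. The percentage in the discordant subset therefore mixes people who are impaired with people who have an ordinary low score. Without the same percentage in another group, the reader cannot tell which dominates. If nobody in the subset were impaired, the table would still report a share of correct DCTclock diagnoses.

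The number of tests also depends on protocol version. The same words define an easier rule for someone with seven tests than for someone with two. If versions are pooled, the percentage would move with the version mix even if DCTclock performed identically in both.

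At stake is the supportive statement that DCTclock is right where it disagrees with MMSE.

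**Working it through.** The protocol gives no expected rate for these rules, so there is no figure of its own to reproduce.

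**Inputs from the protocol.** Seven tests; cut-offs of 2 SD (one test, read as at least one) and 1.5 SD (two or more tests); two tests left under version 2.

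**Assumptions not in the protocol.** Scores are normal, the mean and SD are those of an unimpaired norm, each listed test gives one score, and all pairs of tests share a correlation rho between 0 and 0.7.

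**Per-test tails.** P(Z < -2) = 0.02275; P(Z < -1.5) = 0.0668.

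**Independent tests (rho = 0).**
- Seven tests, at least one 2 SD low: 1 - (1 - 0.02275)^7 = 14.9%.
- Seven tests, two or more 1.5 SD low: 1 - 0.9332^7 - 7 × 0.0668 × 0.9332^6 = 7.5%.
- Two tests, at least one 2 SD low: 1 - (1 - 0.02275)^2 = 4.5%.
- Two tests, both 1.5 SD low: 0.0668^2 = 0.45%.

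**Correlated tests.** One-factor normal model. Given the common factor z, each test falls below cut-off c with probability Φ((c - √rho·z)/√(1 - rho)). The binomial tail is then averaged over z.

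| rho | 7 tests, ≥1 at 2 SD | 7 tests, ≥2 at 1.5 SD | 2 tests, ≥1 at 2 SD | 2 tests, both at 1.5 SD |
|---|---|---|---|---|
| 0 | 14.9% | 7.5% | 4.5% | 0.45% |
| 0.3 | 12.6% | 10.6% | 4.4% | 1.1% |
| 0.5 | 10.6% | 11.2% | 4.1% | 1.8% |
| 0.7 | 8.2% | 10.9% | 3.8% | 2.8% |

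The seven-test rate exceeds the two-test rate by a factor of 2.2 (8.22/3.81) to 3.3 (14.88/4.50) for the 2 SD rule. For the 1.5 SD rule the factor is 3.9 (10.92/2.82) to 16.6 (7.48/0.45).

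**Sensitivity.** If Trails A and B count as separate scores, version 2 has three scores and the 2 SD rule gives 6.7% (rho 0) to 5.0% (rho 0.7). If one test means exactly one, the seven-test rate is 13.9% (rho 0) to 4.6% (rho 0.7). If the mean is that of the whole study sample, about half of it planned from neurology clinics (section 5.3), the rates in unimpaired people would be lower.

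**What a comparison group would show.** These rates are for unselected unimpaired people, whereas the discordant subset is selected for poor DCTclock scores. To see the effect, let everyone be unimpaired and let DCTclock correlate with each test at the same rho as the tests do with each other. Compare the lowest 5% to 20% on DCTclock with the rest (simulation, 2 million draws):
- rho 0.3, lowest 20%: 25.7% have at least one score 2 SD low, against 9.4% in the rest;
- rho 0.5, lowest 5%: 48.5%, against 8.6%.

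Over rho of 0.3 and 0.5 and this range of cut-offs, the selected group runs from about 26% to 49% and the rest from about 6% to 11%. A large difference can arise with nobody impaired.

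**The case against.** **Optional and descriptive.** The inspection may or may not be done, belongs to no stated aim or endpoint, carries no test, and has no success criterion tied to it. This stands and limits the importance of the point.

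**Detail for the SAP.** Norms, comparison columns and handling of incomplete batteries are commonly left to the SAP. This stands for the choice of norms. It does not remove the point, because the protocol itself fixes the subset, the cut-offs, the test list and the interpretation, and the interpretation is the part that fails.

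**One low score does not decide anything.** A reader might infer that the plan lets the loosest rule settle whether DCTclock was right. The document does not say so. It shows three percentages side by side, and the MoCA line, available in both versions, has no multiple-test problem.

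**Pooling of versions is not stated.** A reader might take it as given that version 2 participants are scored on two tests and merged with the others. The when-available clause can equally mean that the seven-test rules are shown only for participants who took those tests. The text is ambiguous, and that is as far as the criticism goes.

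**The rates do not describe the analysed subset.** A reader might treat 8% to 15% as the part of the reported percentage that is false, or treat the excess over a concordant-unimpaired group as the true rate of correct diagnosis. Neither is supported. The subset is selected for low DCTclock scores and the comparison group for good ones, so a correlation between DCTclock and the battery alone produces an excess. This objection stands in full and governs how the fix must be worded.

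**Conclusion.** The point holds as a fault of interpretation in an optional, descriptive analysis. Following section 10.4.10 as written would present ordinary low scores as correct DCTclock diagnoses, with nothing beside them to show how common such scores are.

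The size is about 8% to 15% (one score 2 SD low) and 7% to 11% (two or more 1.5 SD low) in unselected unimpaired people with all seven tests. It is about 4% to 4.5% and 0.5% to 3% with only Digit Span and Trails. These are not protocol figures: they rest on normality, unimpaired norms and a common correlation of 0 to 0.7. The need for a comparison group does not depend on them.

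The calculation does not show that DCTclock is wrong in the discordant cases, and the primary kappa analysis is unaffected. It is a small, worthwhile improvement.

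**What to change.** In section 10.4.10:

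1. Apply the two seven-test rules only to participants given all seven tests, or report them separately by protocol version.
2. Show the same percentages for participants unimpaired on both MMSE and DCTclock, with the difference between the two groups and its 95% CI.
3. Replace the statement of purpose with wording that the difference describes whether DCTclock is associated with low battery scores among MMSE-unimpaired participants. State that it is not a rate of correct diagnosis, since it can be positive with nobody impaired whenever DCTclock correlates with the battery tests.

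The cost is a little extra tabulation from data the study already collects, and a less favourable supportive figure. No new participants or tests are needed.

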#### 10.4.11 MULTIPLE COMPARISON/MULTIPLICITY

Given the nature of the analysis, there will be no adjustment for multiple comparisons.

#### 10.4.12 TABULATION OF INDIVIDUAL RESPONSE DATA

Individual participant scores will be listed for each of DCTclock and MMSE by time point for each participant. Demographic information and adverse events will also be listed for each participant.

### 10.5 MEASURES TO MINIMIZE BIAS

#### 10.5.1 ENROLLMENT/ RANDOMIZATION/ MASKING PROCEDURES

N/A

#### 10.5.2 EVALUATION OF SUCCESS OF BLINDING

N/A

#### 10.5.3 BREAKING THE STUDY BLIND/PARTICIPANT CODE

N/A

## 11 SOURCE DOCUMENTS AND ACCESS TO SOURCE DATA/DOCUMENTS

Each participating site will maintain appropriate medical and research records for this trial, in compliance with regulatory requirements and institutional requirements for the protection of confidentiality of participants. Each site will permit authorized representatives of the sponsor and regulatory agencies to examine (and when permitted by applicable law, to copy) clinical records for the purposes of quality assurance reviews, audits, and evaluation of the study safety, progress, and data validity.

Source data are all information, original records of clinical findings, observations, or other activities in a clinical trial necessary for the reconstruction and evaluation of the trial.

## 12 QUALITY ASSURANCE AND QUALITY CONTROL

QC procedures will be implemented. Any missing data or data anomalies will be communicated to the site(s) for clarification/resolution.

Following written SOPs, the monitors will verify that the clinical trial is conducted and data are generated, documented (recorded), and reported in compliance with the protocol, GCP, and the applicable regulatory requirements.

The investigational site will provide direct access to all trial related sites, source data/documents, and reports for the purpose of monitoring and auditing by the sponsor, and inspection by local and regulatory authorities.

## 13 ETHICS/PROTECTION OF HUMAN SUBJECTS

### 13.1 ETHICAL STANDARD

This study will be performed in accordance with the relevant parts of the Code of Federal Regulations, ICH Guidelines for Good Clinical Practice (GCP), the Declaration of Helsinki and any other applicable regional and/or national regulations.

